11.3. Adverse events of special interest

11.3.1. Use of "sick days"

As per the protocol each site will have a set of sick day rules where certain AEs will result in emergency hydrocortisone being taken.

All AEs leading to use of "sick day rules" will be summarised (frequency and percentage of subjects) by SOC, PT, previous treatment, feeder study and overall DIUR-006 study.

In addition, all AEs leading to use of "sick day rules" will also be summarised (frequency and percentage of subjects) by preferred term, route, and specific sick day medication by treatment group.

There will be a separate listing showing details of all AEs leading to use of sick day rules and specific sick day medication.

11.3.2. Adrenal crises

All AEs leading to adrenal crises as defined in the protocol will be summarised (frequency and percentage of subjects) by SOC, PT, previous treatment, feeder study and overall DIUR-006 study. There will be a separate listing showing details of all AEs leading to adrenal crises.

The adrenal crisis rate per 100 subject years will be presented for overall subjects and by feeder study and previous treatment. This table shall display the total number of adrenal crises on study, the number of subject years on study, and the number of subjects who have experienced at least one adrenal crisis on study.

A separate listing will display all subjects who have experienced at least one adrenal crisis, along with the number of adrenal crisis events experienced on study, the number of days on study, the subject's number of adrenal crises per 100 subject years and the mean number of adrenal crises per 100 patient years in this study for the subject's feeder study group.

11.3.3. Unexpected therapeutic benefit

All AEs of unexpected therapeutic benefit will be summarised (frequency and percentage of subjects) by PT, LLT and treatment group. There will be a separate listing showing details of all AEs of unexpected therapeutic benefit.

11.4. Routine clinical laboratory evaluations

11.4.1. Naming conventions

The laboratory test names will be displayed using test names consistent with the protocol for all reporting. Study Data Tabulation Model (SDTM) standard names will be derived in the dataset, but not displayed. Where needed, an abbreviated version of the laboratory test names may be displayed.

A full list of laboratory display names (full and an acceptable abbreviation) together with their SDTM laboratory test code and name is given in Appendix B for haematology, clinical biochemistry, bone markers and laboratory parameters of special interest.

11.4.2. Haematology

The following haematology parameters will be collected:

Red blood cell count (RBC), red cell distribution width (RDW), haemoglobin (Hb), haematocrit (Hct), mean corpuscular volume (MCV), mean cell haemoglobin (MCH), mean cell haemoglobin

Version: 6.0 12 July 2022

concentration (MCHC), platelet count (PLT), white blood cell count (WBC), WBC differential count: neutrophils, eosinophils, basophils, lymphocytes, monocytes (absolute).

All laboratory analyses will be carried out by the central laboratory. If laboratory results are needed urgently for safety reasons during the study, these can be processed at the local laboratory and the results recorded in the electronic case report form (eCRF). For the local lab data, the local reference ranges will be used and if for any reason these are missing, the central ranges will be used, with any such occurrences clearly marked in the listings. Change from pre-Chronocort® baseline (see Section 9.3.2) will be calculated at each visit (every 6 months from baseline) and summary statistics will be presented for both absolute values and change from baseline for all haematology parameters by previous treatment group, scheduled visit, feeder study and overall DIUR-006 study. Shift tables of baseline to minimum and maximum on-treatment will be produced for the appropriate parameters displaying the number and percentage of subjects in each of the categories (High, Low and Normal) relative to the category of their baseline assessment. Haematology results considered clinically significant by the investigator will be summarised. Detailed listings will be produced for all haematology parameters. In addition, boxplots of change from pre-Chronocort® baseline in haematology parameters over time will be produced along with a line connecting the mean change through time.

For the purpose of both Listings and Summary Tables, the haematology results will be divided into the following groups of related items:

Haematology (1)

- Red blood cell count (RBCs)
- haemoglobin (Hb)
- haematocrit (Hct)

Haematology (2)

- red cell distribution width (RDW)
- mean corpuscular volume (MCV)
- mean cell haemoglobin (MCH)
- mean cell haemoglobin concentration (MCHC)
- platelet count (PLTs)

RDW-CV(%) will be provided by the central laboratory. If any local laboratories provide RDW-SD (fL) measurements, RDW-CV(%) will be calculated from the RDW-SD (fl) and MCV measurements using the formula:

• RDW-CV(%) = (RDW-SD(fL)/MCV)*100.

Haematology (3)

- total white blood cell count (WBCs)
- lymphocyte count
- monocyte count
- neutrophil count
- basophil count eosinophil count

White blood cells (Leukocytes) are made up of Neutrophils + Eosinophils + Basophils +Lymphocyte + Monocyte

Therefore, to express any of the components as a percentage of Leukocytes, the formula is:

Version: 6.0 12 July 2022

Components cell count/Leukocytes counts*100, (e.g. Neutrophils count/Leukocytes counts*100)

However, if the percentage is given and to derive the cell count, the formula is:

• (Components percentage/100)*Leukocytes counts, (e.g. (Neutrophils % /100)*Leukocytes counts)

Note it is important that the component cell count and white blood cell count (Leukocytes) are expressed in the same units when applying these derivations.

11.4.3. Clinical biochemistry

The following routine biochemistry parameters will be collected:

Sodium, potassium, chloride, total carbon dioxide (CO₂), creatinine, glucose, blood urea nitrogen (BUN), albumin, total calcium, total magnesium, inorganic phosphorus, alkaline phosphatase, alanine aminotransferase (ALT/GPT), aspartate aminotransferase (AST/GOT), total bilirubin, direct bilirubin, lactate dehydrogenase (LDH), total protein, total creatine kinase (CK), uric acid, total cholesterol, high density lipoprotein (HDL) cholesterol, low density lipoprotein (LDL) cholesterol, triglycerides.

All laboratory analyses will be carried out by the central laboratory . If laboratory results are needed urgently for safety reasons during the study, these can be processed at the local laboratory and the results will be recorded in the eCRF. For the local lab data, the local reference ranges will be used and if for any reason these are missing, the central ranges will be used, with any such occurrences clearly marked in the listings.

Change from baseline will be calculated at each visit (every 6 months from baseline) and summary statistics will be presented for both absolute values and change from baseline for all clinical biochemistry parameters by previous treatment, scheduled visit, feeder study and overall DIUR-006 study. Shift tables of baseline to minimum and maximum on-treatment will be produced for the appropriate parameters displaying the number and percentage of subjects in each of the categories (High, Low and Normal) relative to the category of their baseline assessment. Biochemistry results considered clinically significant by the investigator will be summarised. Detailed listings will be produced for all routine biochemistry parameters. In addition, boxplots of change from pre-Chronocort® baseline in clinical biochemistry parameters over time will be produced along with a line connecting the mean change through time.

For the purpose of both Listings and Summary Tables, the clinical biochemistry results will be divided into the following groups of related items:

Biochemistry (1)

- Sodium
- potassium
- chloride
- total CO₂
- total calcium
- total magnesium
- inorganic phosphorus

Biochemistry (2)

creatinine

- blood urea nitrogen (BUN)
- glucose
- uric acid
- total protein
- albumin

Biochemistry (3)

- alkaline phosphatase
- ALT/GPT
- AST/GOT
- total creatine kinase
- lactate dehydrogenase
- total bilirubin
- direct bilirubin

Biochemistry (4)

- total cholesterol
- high density lipoprotein (HDL) cholesterol
- low density lipoprotein (LDL) cholesterol
- triglycerides

11.4.4. Urinalysis

A pregnancy test will be carried out in female subjects of child bearing potential at each visit (Week 4, Week 12, Week 24, and then every 6 months) and the results will be listed.

11.5. Vital signs

The following vital signs will be collected at baseline and every 6 months: systolic blood pressure (SBP), diastolic blood pressure (DBP), pulse rate, respiratory rate, temperature, waist circumference, weight, BMI.

The change from baseline will be calculated and summary statistics will be tabulated for both absolute values and change from baseline by previous treatment, scheduled visit, feeder study and overall DIUR-006 study. Shift tables will be created for the following vital signs: SBP and DBP. In addition, boxplots of change from pre-Chronocort® baseline in vital signs over time will be produced along with a line connecting the mean change through time.

The intra-subject/within-subject change from baseline in subject weight shall also be presented at each visit and this subject-level change from baseline shall also be displayed visually in a spaghetti plot for this parameter.

Vital signs will be listed and abnormal findings will be marked.

12. Other safety analyses

12.1. Physical examination

Abnormal findings from the full physical examination at baseline and every 6 months will be tabulated by body system, previous treatment, feeder study, overall DIUR-006 study and visit

Version: 6.0 12 July 2022

showing the frequency and percentage of subjects with an abnormal finding. Abnormal physical examination results will be listed, together with an indication of whether or not that finding was clinically significant.

12.2. Concomitant medications excluding glucocorticoid steroids

Concomitant medications excluding glucocorticoid steroids^[a], which include medications that began prior to entering Study DIUR-006 but were ongoing after the first dose of Chronocort® in Study DIUR-006, will be summarised descriptively by ATC text, previous treatment, feeder study and overall DIUR-006 study using counts and percentages as appropriate. A detailed listing of concomitant medications excluding steroids will be produced.

^[a] The following list of steroids will be excluded from the summaries and listings of concomitant medications and instead will be reported under sick day medications and steroids taken in addition to IMP (see section 12.3).

ATCCODE	LEVEL	ATC Text
D07AC	4	Corticosteroids, potent (group III)
D07AD	4	Corticosteroids, very potent (group IV)
H02	2	CORTICOSTEROIDS FOR SYSTEMIC USE
H02A	3	CORTICOSTEROIDS FOR SYSTEMIC USE, PLAIN
H02AA	4	Mineralocorticoids
H02AB	4	Glucocorticoids ^[b]
H02B	3	CORTICOSTEROIDS FOR SYSTEMIC USE, COMBINATIONS
H02BX	4	Corticosteroids for systemic use, combinations
R01AD	4	Corticosteroids
R03BA	4	Glucocorticoids
S01BA	4	Corticosteroids, plain
S02B	3	CORTICOSTEROIDS
S02BA	4	Corticosteroids
S03B	3	CORTICOSTEROIDS
S03BA	4	Corticosteroids

[[]b] Excluding Fludrocortisone, which will be summarised alongside concomitant medication.

12.3. Use of dispensed sick day medications and steroids taken in addition to IMP

Use of dispensed sick day medications by route and drug name and steroids taken in addition to IMP (which includes medications that began prior to the date of randomisation but were ongoing after first dose of randomised treatment or started after randomised treatment) by ATC text and generic term will be summarised by treatment group.

A detailed listing of all dispensed sick day medications and steroids taken in addition to IMP will be produced.

Version: 6.0 12 July 2022

13. Secondary efficacy analyses

13.1. Extent of exposure

Summary statistics will be presented for both the total duration and actual duration of exposure to Chronocort® in days. For subjects randomised to Chronocort® in DIUR-005 who immediately enter DIUR-006, exposure to Chronocort® during the DIUR-006 study period and continuous cumulative exposure including any immediate exposure prior to DIUR-006 will be considered. Whereas for subjects from DIUR-003 and DIUR-005 gap subjects, exposure during the DIUR-006 will only be derived as this is the only period of time where Chronocort® is taken continuously.

Total treatment duration in DIUR-006 only will be calculated as follows:

Date of last dose of Chronocort® in DIUR-006 – Date of first dose of Chronocort® in DIUR-006
 + 1.

Actual treatment duration in DIUR-006 only will consider dose interruptions and will be:

• The total number of days in which the subject took at least one dose of Chronocort® in DIUR-006.

Cumulative total treatment duration, which includes the exposure prior to DIUR-006 for those subjects who received Chronocort® in DIUR-005 and immediately entered DIUR-006, will be calculated as follows:

 Date of last dose of Chronocort® in DIUR-006 - Date of first dose of Chronocort® in either DIUR-005 or DIUR-006 + 1.

Cumulative actual duration will consider dose interruptions during DIUR-005 and DIUR-006, for subjects who received Chronocort® in DIUR-005 and immediately entered DIUR-006 only. It will be calculated as:

• The total number of days in which the subject took at least one dose of Chronocort® in either DIUR-005 or DIUR-006.

Any planned or unplanned dose titration decisions which are made by the investigating physician will be summarised by overall DIUR-006 study, feeder study and previous treatment and visit (e.g. planned dose titration Visit 1-2/ Baseline-Week4; planned dose titration Visit 2/Week 4; planned dose titration Visit 2-3/ Week4-Week12; planned dose titration Visit 3/Week 12 and so on). A separate category will be used to summarise any unplanned dose titrations at any timepoint during the study. The summary will show frequency and percentage of subjects requiring a dose adjustment, as well as the dose adjustment required (increase morning dose, increase evening dose, increase evening dose, decrease morning and evening dose.

A summary of the number and percentage of subjects with dose increases, reductions and interruptions will be produced and will be broken down by the reason for dose increases, reductions and interruptions. It will also show the number of dose increases, reductions and interruptions per subject as well as the mean and the standard deviation.

The number and percentage of subjects receiving Chronocort® at each dose distribution level (in mg) at their last daily dose shall be presented, with the number of subjects reported overall and by their feeder study and previous treatment.

All treatment exposure data will be listed in detail.

Version: 6.0 12 July 2022

Summary statistics for the total daily dose of Chronocort® in mg/day will be presented in terms of hydrocortisone based on the dose instructed by the investigator, by previous treatment and feeder study. Statistics will be grouped into time intervals, where each interval is defined as the period of time between scheduled visits (e.g. Baseline to Week 4; Week 4 to Week 12; Week 12 to Week 24 etc). Summary statistics will present the total daily dose of Chronocort®, in terms of hydrocortisone equivalent, per body surface area by treatment group. Dosing periods can be of differing lengths due to titration events. Therefore, the total daily dose will be calculated by considering the duration of time a patient is instructed to take a given quantity of Chronocort®:

$$Total\ Daily\ Dose = \frac{\sum_{i=1}^{N}(Dose_{i}*Duration_{i})}{\sum_{i=1}^{N}Duration_{i}}$$

For i = 1, 2, ..., N titration events. Where $Dose_i$ is the assigned quantity of Chronocort® at the i-th titration event and $Duration_i$ is the duration of exposure of the dose assigned at the i-th titration event.

Additionally, the total daily dose per body surface area of Chronocort® (mg/day/m²) will be

$$\frac{\textit{Total daily dose of Chronocort}^{\circledR} (\textit{mg/day})}{\textit{Body Surface Area } (\textit{m}^2)}$$

The calculation for body surface area will use the Dubois formula as provided in Section 10.3.

13.2. 17-OHP and A4 levels

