### 10.6 Permitted Concomitant Medications/Treatments

The subjects must be instructed that no additional medication is allowed without the prior consent of the investigator. Any medication considered necessary for the subject's safety and well-being may be given at the discretion of the investigator. Medication for sick days does not require authorisation but any use of the safety pack medication must be recorded in the eCRF. All concomitant medications and treatments will be recorded in the subject's eCRF.

If a participant has received the severe acute respiratory syndrome coronavirus 2 (SARS-CoV-2/COVID-19) vaccine then the next visit must be scheduled at least 5 days post-vaccine. If the participant experiences any side effects from the COVID-19 vaccine then they should take additional stress doses in line with the "sick day rules" (see Appendix 3 - Sick Day Rules). If a stress dose is taken within 5 days of a scheduled visit, then the visit should be delayed until the participant has had a 5-day period without use of any stress doses.

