#### 11.1.12 Unscheduled Visits or telephone calls

If any unscheduled visits are required, e.g. to follow up on an AE, then the details should be recorded in the eCRF, along with the results of any tests carried out. If laboratory results are needed urgently these can be processed at the local laboratory (note that the local laboratory normal reference ranges will then be needed). Additional telephone calls may also be required in between visits to maintain contact with the subject and to ensure AEs and use of any sick day rules are being noted. Any information collected in such calls must be recorded in the eCRF.

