## 11.3 Sick Day Rules

All subjects will be educated regarding "sick day rules". "Sick day rules," a written guideline regarding what to do during any illness, will be given to the subjects (as is done for all CAH subjects). Where sites have a standard set of "sick day rules" these will be supplied to subjects at that site routinely along with an emergency pack of medication (see Appendix 3 for an example of sick day rules that can be used for this study if a site choses to do so). Use of sick day rules will be recorded in eCRF, including both duration, dose of steroid and use of injection. Sick day rules from each site will be collected prior to the beginning of recruitment and placed on file by the Sponsor.

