#### 13.1.2 Hypothesis Testing and Confidence Intervals

Since all subjects participating in this trial will be receiving Chronocort®, there will be no formal treatment comparisons. Summaries over time will be produced for safety and efficacy parameters.

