#### 13.7 Power and Sample Size Considerations

Since this is an open label extension study to gather long term safety and efficacy data on Chronocort®, no formal power or sample size calculations have been performed. All eligible subjects from study DIUR-003 (16 subjects) and DIUR-005 (122 subjects) may enter this study, giving a maximum of 138 subjects. Subjects from study DIUR-003 can be enrolled at any time (since this study has been completed), but subjects from study DIUR-005 will be enrolled when they complete Visit 4 of study DIUR-005. However, in some cases there may be a delay between a subject completing study DIUR-005 and starting study DIUR-006 during which the subject receives standard glucocorticoid therapy. In this case the subject should be entered into study DIUR-006 as soon as possible. All subjects must be enrolled by 31 October 2018, with no subjects allowed to enter the study after this date.

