10.2. Protocol deviations

Any deviations from the protocol will be reviewed at the Data Review Meeting but prior to database lock. Each protocol deviation will be classified as either 'minor' (unlikely to affect trial outcomes) or 'major' (likely to affect outcomes). Subjects with major protocol deviations will not lead to exclusion from the full analysis set. In addition, protocol deviations will be grouped into the following high-level categories:

- Inclusion criteria subject failed to meet all inclusion criteria,
- Exclusion criteria subject met at least one exclusion criteria,
- Study procedure site or subject did not follow procedures specified in protocol,
- Titration site or subject deviated from the titration process,
- Treatment Chronocort® not taken as per protocol,
- NIMP subject used an unauthorised Non Investigational Medicinal Product,
- Drug Accountability subject or site failed to account for all Investigation Medicinal Product,
- Safety Reporting site or subject did not follow safety reporting procedures,
- Informed Consent site or subject did not correctly document informed consent,
- Other any other protocol deviations not fitting into the categories outlined above.

Protocol deviations will be listed and summarised by overall DIUR-006 study, feeder study, previous treatment, by classification (major or minor) and protocol deviation category. The listing will also show whether protocol deviations were related to COVID-19 or not. Additionally, a separate summary of COVID-19 related protocol deviations will be produced.

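### The SAP has no analysis counterpart to the protocol's 5-day stress-dose rule for hormone samples, and no planned summary totals glucocorticoid in mg

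*SAP*

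**What the plan says.** **Hormone samples.** Protocol 10.6 covers scheduled visits that would follow a stress dose by 5 days or less: "then the visit should be delayed until the participant has had a 5-day period without use of any stress doses". Protocol 11.1.2, 11.1.3, 11.1.5, 11.1.7 and 11.1.10 apply the same postponement to the baseline, Week 4, Week 12, 6-monthly and final visits. Protocol 11.1.12 covers unscheduled visits, for example to follow up an AE. Their details go into the eCRF "along with the results of any tests carried out", and that section states no 5-day condition.

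In the SAP, 9.1 deals with missing hormone values only. Where several visits, unscheduled ones included, fall in one analysis window, 9.3.1 takes the one nearest the target day, and the earlier one if they tie. On deviations, SAP 10.2 states: "Subjects with major protocol deviations will not lead to exclusion from the full analysis set". SAP 13.2.1 scores control against the Table 8 ranges and also counts subjects with 09:00 17-OHP below 36.4 nmol/L.

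**Dose.** SAP 13.1 says the "total daily dose of Chronocort® in mg/day will be presented in terms of hydrocortisone based on the dose instructed by the investigator". In its formula the dose term "is the assigned quantity of Chronocort® at the i-th titration event". The dose per body surface area is this figure divided by BSA. Protocol 10.5 keeps Chronocort going during stress dosing and has extra hydrocortisone taken from the safety pack, so rescue comes on top. Protocol 11.3 states: "Use of sick day rules will be recorded in eCRF, including both duration, dose of steroid and use of injection". SAP 12.3 summarises sick-day medication by route and drug name, and other added steroids by ATC text and generic term. It asks for no amount in mg.

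**The concern.** The protocol treats a hormone value taken soon after a stress dose as unsuitable for a scheduled visit. The analysis plan does not carry that judgement through to the values it tabulates. If a 17-OHP or A4 result lowered by added glucocorticoid is used as the visit value, it may be counted as disease control on Chronocort.

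The dose tables are efficacy summaries, and the primary objective includes over-treatment. A reader who takes the Chronocort dose for the whole glucocorticoid burden would miss whatever was taken as rescue or prescribed for other reasons. The recorded data would allow a total, but none is planned.

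**Working it through.** The study is descriptive: "no formal power or sample size calculations have been performed" and "there will be no formal treatment comparisons". There is therefore no planned figure to reproduce, and no power or error rate depends on this point.

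**A. Can a sample taken under stress dosing become the visit value?**

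1. Take Visit 5 from SAP Table 7: target day 365, range 281 to 449.
2. Suppose stress dosing runs over the target day, with the last stress dose on day 365 or later. The postponed scheduled visit then falls on day 365 + 5 = 370 at the earliest, at least 5 days from target.
3. An unscheduled sample on any of days 361 to 369 is at most 4 days from target, so it is nearer. One on day 360 ties with a visit on day 370, and the tie goes to the earlier. All these days lie inside the range.
4. The SAP 9.3.1 rule therefore selects the unscheduled sample. Postponement for illness makes this more likely, because it moves the scheduled visit away from the target.

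Two further routes need no unscheduled visit. A scheduled sample drawn in breach of the 5-day rule stays in, because SAP 9.1 sets aside nothing on this ground and SAP 10.2 keeps the subject. A systemic steroid course given for another reason is outside the 5-day rule, which names only stress doses and sick-day rules. SAP 12.2 lists ATC group H02 among the steroids to be reported, so the plan foresees such use.

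How the value is then scored:

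| Table | Lower limit | Upper limit |
|---|---|---|
| 17-OHP optimal range | 1.2 nmol/L | 36.4 nmol/L |
| A4, males | 1.4 nmol/L | 5.2 nmol/L |
| A4, females | 1.0 nmol/L | 7.0 nmol/L |
| 17-OHP at 09:00, separate count | none | below 36.4 nmol/L |

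Moderate suppression can move a value into range. Strong suppression can take it below the lower limit, where it scores as not controlled. Only the last row counts every suppressed value as success. One value that would otherwise be uncontrolled moves a visit's rate by 1/138 = 0.7 percentage points if all 138 possible subjects have a value, or 1 point if 100 do.

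**B. How much glucocorticoid is outside the dose table?**

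Inputs:
- Stress dose of 3 × 10 = 30 or 3 × 20 = 60 mg/day oral hydrocortisone (Protocol Appendix 3, an example; sites may use their own rules).
- Reference Chronocort dose of 26 mg/day (DIUR-003 mean, Protocol 5.5) or 30 mg/day (maximum converted starting dose, Protocol 11.1.2).
- Stress days: not in the documents, so assumed. Injections are left out.

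Formula: added mg/day = stress dose × stress days / interval days.

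| Assumed stress days | Interval | Added mg/day | Share of 26 mg | Share of 30 mg |
|---|---|---|---|---|
| 0 | any | 0 | 0% | 0% |
| 10 | 365 days | 0.8 to 1.6 | 3.2 to 6.3% | 2.7 to 5.5% |
| 20 | 365 days | 1.6 to 3.3 | 6.3 to 12.6% | 5.5 to 11.0% |
| 5 | 28 days (Baseline to Week 4) | 5.4 to 10.7 | 21 to 41% | 18 to 36% |

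Example: 10 × 30 / 365 = 0.82 and 10 × 60 / 365 = 1.64. To reach 5% of 30 mg/day (1.5 mg/day) over a year takes 1.5 × 365 / 30 = 18 days at 30 mg, or 9 days at 60 mg.

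The gap is small for an average year with few stress days. It can be large for one subject in a short interval.

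**The case against.** The protocol already protects nearly all hormone data, since every scheduled visit is postponed until 5 days after stress dosing. An unscheduled visit matters only if it carries a 17-OHP or A4 sample, falls in a window and lies nearer the target. Protocol 8.1 discourages repeat androgen testing at unscheduled dose adjustments. Other medication needs the investigator's consent, and regular daily steroids for other indications are an entry exclusion. SAP 9.4 and 10.2 send extreme values and deviations to the Data Review Meeting, and Appendix A lists hormone and dose tables without extreme cases. The text of SAP 8.3, which the revision history says covers those analyses, was not available for this check.

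Most of this stands, and it is why affected samples are probably few. It does not close the gap. A suppressed value inside the range is not an outlier, and review at a meeting is not a stated rule. If SAP 8.3 defines extreme cases by steroid use, part of the first fix is already met.

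On dose, the tables are labelled as Chronocort dose, which is what the endpoint says. Sick-day use is itself a primary endpoint, with AE overview rows, tables by preferred term, route and medication (SAP 11.3.1), and listings. All of that stands; only the amount in mg is missing.

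A reader might infer that both sets of tables are biased in favour of the product, or that the dose table would show a steroid saving that did not occur. The documents support neither. The control ranges have lower limits, the SDS is unsigned so that over-suppression also counts, there is no comparator, and the dose table has no pre-Chronocort row against which to show a saving.

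**Conclusion.** A modest gap that is cheap to close. The SAP does not apply the protocol's own 5-day criterion to the values it analyses, and its nearest-to-target rule can prefer an illness-time sample to a postponed scheduled one. Such a value can be scored as control on Chronocort, most clearly in the <36.4 nmol/L table. The number of affected samples cannot be derived from the documents.

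The dose and dose-per-BSA tables are right for what they claim. They should not be read as total steroid need, because no planned summary gives that in mg. With an assumed 10 stress days a year at 30 to 60 mg, the unreported addition is about 0.8 to 1.6 mg/day. This rests on the Appendix 3 example doses, oral use only, and Chronocort continued throughout.

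It may be tempting to compare total on-study glucocorticoid with the pre-Chronocort dose. That would not be like for like: Protocol 11.1.2 records the last glucocorticoid dose before a visit held at least 5 days clear of sick-day dosing, so rescue is absent from it by design.

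**What to change.** 1. In SAP 9.1, 9.3.1 and 13.2, flag any 17-OHP or A4 sample taken within 5 days after a recorded stress dose or other systemic glucocorticoid. Do not let a flagged unscheduled sample replace a scheduled visit. Repeat the disease-control tables, including the <36.4 nmol/L table, with flagged values set to missing.
2. Add a supplementary on-study table by interval: Chronocort plus recorded sick-day and other systemic glucocorticoid, in hydrocortisone equivalents. Use the SAP Table 4 factors where available and list any steroid without a factor. Keep the existing Chronocort tables as they are.
3. If a pre-Chronocort dose row is shown, label it as maintenance dose and compare it only with the on-study Chronocort maintenance dose, not with the total including rescue.

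Cost: SAP wording, one flag, one extra derivation and one extra table, from data the protocol already has recorded. The repeated control tables will have a few more missing hormone values. No visit, dosing or rescue rule changes.
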